5.2 Exclusion Criteria

Subjects will be excluded from participation in the study if they meet any of the following criteria:

- a) The Subject is a woman who is pregnant or lactating.
- b) Contralateral knee has already been enrolled in this study³.
- c) Revision knee that was previously enrolled in the study as a primary knee (ipsilateral).
- d) Subject has participated in a clinical study with an investigational product (drug or device) in the last two (2) years.
- e) Subject has had surgery on their contralateral knee within six (6) months of study enrolment or has surgery planned on their contralateral knee less than six (6) months of the study surgery.
- f) Subject is suffering from inflammatory arthritis in any joint (e.g., rheumatoid arthritis, juvenile rheumatoid arthritis, psoriatic arthritis, systemic lupus erythematosus, etc.).
- g) Active local or systemic infection.
- h) Loss of bone or musculature, inadequate bone quality (e.g. severe osteoporosis), neuromuscular compromise or vascular deficiency at the bone site in the affected limb in sufficient degree to render the procedure unjustifiable (e.g. absence of musculoligamentous supporting structures that could lead to implant instability, joint neuropathy).
- i) Severe instability secondary to advanced loss of osteochondral structure or the absence of collateral ligament integrity.
- j) The inability to make bone cuts (e.g. inadequate bone stock) so as to assure correct component position, a firm press fit, and intimate apposition of the cut bone and prosthetic surfaces.
- k) Subject is currently involved in any personal injury litigation, medical-legal or worker's compensation claims.
- Subject, in the opinion of the Investigator, is a drug or alcohol abuser (in the last five 5 years) or has a
 psychological disorder that could affect their ability to complete patient reported questionnaires or
 be compliant with follow-up requirements.

5.3 Definition of Subject Enrolment

A patient will be considered enrolled when they have provided written informed consent to participate in this Investigation, which includes authorization of the release of their Personal Health Information (PHI).

² Note the AKS may not be available in all required languages – if there is no translation available for the Subject's primary language then that Subject need not complete that particular eCRF.

⁴ This study does not permit enrolment of any subject undergoing simultaneous bilateral knee surgery. If the subject plans staged bilateral knee surgery, the surgeries must be 6 months apart and first knee will be enrolled into this study.

6 OBJECTIVES

6.1 Primary Objective

The primary objective of this clinical investigation is to evaluate functional responder rates with an objective performance criteria (OPC) of 85% as measured by the KOOS questionnaire for the first 225 tibia (CR FB and PS FB combined) implanted with the ATTUNE Cementless FB tray (primary and revision procedures) and will be analyzed when these patients have passed the 1 year preferred post-op window. Study success will be determined using the primary TKA (CR FB and PS FB combined) analysis group.

6.2 Secondary Objectives

The secondary objectives of this study are to establish the surgical effectiveness of the ATTUNE Cementless Tibial Base by evaluating:

- Type and frequency of Adverse Events and Device Deficiencies.
- Functional responder rates with an objective performance criteria (OPC) of 85% as measured by the KOOS questionnaire for all subjects at the 1-year timepoint.
- The change from preoperative baseline to the 6-week, 6-month, 1-year, 2-year and 5-year timepoints in functional outcomes and quality of life assessments, as measured using additional patient reported outcomes measures (PROMS):
 - o AKS (2011)
 - KOOS (all subscores)
 - o FJS-12 (post-op only)
 - o *EQ-5D-5L*
- Implant survivorship of the ATTUNE Cementless FB Tibial Base using Kaplan-Meier survival analysis at 1, 2 and 5-year timepoints.
- Investigator-conducted radiographic analysis of the tibial and patellar components at 6 weeks/6 months 1, 2 and 5 years after surgery.

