8.5 Post-operative Withdrawal of Enrolled Subjects

A post-operative withdrawal is a Subject who has signed the Informed Consent Document (ICD), has been implanted with a study device, and is later withdrawn from study participation (i.e., withdrawal of consent, revision of any study TKA component, death, etc.). Table 8-9 describes post-operative withdrawal scenarios and the eCRF to be completed. Further description of revision is provided in Section 8.6 Revisions. No data after the date of withdrawal will be included in the clinical analysis.

Table 8-9: Post-operative Withdrawal Scenarios

Example	Action	Follow Up
Subject withdraws consent	 Study site documents Subjects' request for withdrawal from study. Complete Study Completion/Discontinuation eCRF 	Do not continue
Surgeon preference / medical opinion	 Study site documents Surgeons' reason for patient withdrawal from study (should occur under very limited conditions, in order to avoid investigator bias). Complete Study Completion/Discontinuation eCRF 	Do not continue
Death	Complete Adverse Event eCRF Complete Study Completion/Discontinuation eCRF	Do not continue
Revision	See Section 8.6 and Table 8-10 Revision Examples	

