8.6 Revisions

A "revision" is defined as a surgical procedure of the affected knee where one or more of the TKA components (metal femoral component and/or metal tibial base, polyethylene insert, or patella polyethylene resurfacing component) are removed. Should it be necessary for the Subject to undergo a revision of any ATTUNE Cementless Femoral and/or Tibial Base component between the time of enrolment and completion of the study data acquisition, the Subject is to be withdrawn from study participation. Thus, both an Adverse Event (AE) eCRF and the Subject Completion/Discontinuation eCRF must be completed (see Table 8-9). Note that if a tibial insert is exchanged and/or a resurfaced patella is revised, but both the femoral and tibial base components remain, then an AE eCRF must be completed, but the subject is not to be withdrawn from the study.

A "re-operation" is defined as any surgical procedure of the affected knee in which none of the TKA components are removed. Examples include irrigation & debridement without tibial insert exchange or the resurfacing of a previously unresurfaced patella. These subjects are not to be withdrawn. An Adverse Event (AE) eCRF must be completed.

Table 8-10: Revision and Reoperation Examples

Example	Actions	Follow Up
Removal / revision of metal Tibial Base and/or Femoral component	 Complete Adverse Event eCRF Complete Revision/Reoperation eCRF Complete Study Completion/Discontinuation eCRF 	Do not continue
Tibial Insert polyethylene exchange	Complete Adverse Event eCRF Complete Revision/Reoperation eCRF	Continue
Revision of a previously resurfaced patella	 Complete Adverse Event eCRF Complete Revision/Reoperation eCRF 	Continue
Resurfacing of a previously unresurfaced patella in combination with a Tibial polyethylene exchange	 Complete Adverse Event eCRF Complete Revision/Reoperation eCRF 	Continue

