9.5 Handling of Missing Data

Only actual data will be analyzed; there will be no imputation of missing data.

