9.6 Analysis Sets

The following analysis sets are defined for the purpose of analysis: an Intent to Treat (ITT) analysis set, a Safety analysis set, and a Per Protocol (PP) analysis set. The analyses of adverse events and the Kaplan-Meier analysis of revisions will be carried out on the Safety analysis set. The primary endpoint analysis and all secondary endpoint analyses will be carried out on the Per Protocol analysis set. The analysis of the tertiary endpoints will be carried out on the PP analysis set unless otherwise stated in the final clinical summary report.

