9.6.3 PP Analysis Set

The Per Protocol (PP) analysis set is a subset of the Safety analysis set that includes all subjects who meet the following criteria:

- There are no clinically meaningful deviations from the protocol eligibility criteria, and
- The subject receives an ATTUNE Cementless FB tibial base,
- The subject has at least one post-operative evaluation in the 6 week or later time window.

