9.8.1 General Conventions

All analysis will be performed using SAS v9.4 or higher. Statistical summaries (tallies and percentages for categorical variables, and sample size, mean, standard deviation, minimum and maximum (and others as needed) for continuous variables) at each respective time point, or cumulatively for safety endpoints.

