9.8.4.2 Secondary Endpoints and Associated Hypotheses

The secondary endpoints in this study are:

- Type and frequency of Adverse Events and Device Deficiencies.
 - Functional responder rates with an objective performance criteria (OPC) of 85% as measured by the KOOS questionnaire for all subjects (CR FB and PS FB combined) at the 1 year timepoint.
- The change from preoperative baseline to the 6 week, 6 month, 1 year, 2 year and 5 year timepoints in functional outcomes and quality of life assessments, as measured using additional patient reported outcomes measures (PROMS):
 - o AKS 2011
 - KOOS (all subscores)
 - FJS-12 (changes post-operatively only)
 - o *EQ-5D-5L*
- Implant survivorship of the ATTUNE Cementless FB Tibial Base using Kaplan-Meier survival analysis at 1, 2 and 5 year timepoints.
- Investigator-conducted radiographic analysis of the tibial and patellar components at 6 weeks/6 months, 1, 2 and 5 years after surgery.

All secondary endpoint analyses may be conducted after all patients have passed the recommended study window (ex. with a 2-year follow-up analysis conducted after all subjects have passed 790 days post-op). All analyses at these time points will be conducted again with final data, along with endpoints which have a 5-year follow-up time point, with locked data at the close of the study.

A Kaplan-Meier survivorship model will be used to estimate survivorship rates (where a revision is defined in Section 8.6) along with a two-sided, log-log based 95% confidence intervals; this analysis will be conducted on the Safety analysis set.

The types and frequencies of adverse events that occur throughout the study will be tabulated by MedDRA system organ class (SOC) and preferred term (PT) for all Subjects in the Safety analysis set. The proportion of Subjects experiencing each complication (PT within SOC) will be presented, and a 95% confidence interval will be estimated with the binomial exact method.

All other specified secondary endpoints will be presented with statistical summaries at each respective time point; these secondary endpoint analyses will be carried out with all data on subjects in the Per Protocol analysis set.

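### Mean PROM change at 2 and 5 years is planned only as observed-case summaries, so the later means describe the subjects who remain and are too favourable if those doing worse leave

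*Combined protocol and SAP*

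**What the plan says.** The objective in Section 6.2 is "The change from preoperative baseline to the 6-week, 6-month, 1-year, 2-year and 5-year timepoints in functional outcomes and quality of life assessments", covering AKS, KOOS and EQ-5D-5L. FJS-12 is collected only after surgery, and Table 6-1 measures its change from the first post-operative visit.

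The analysis is set out in four places:

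- Section 9.8.4.2: "All other specified secondary endpoints will be presented with statistical summaries at each respective time point".
- Section 9.8.1 lists the contents of those summaries: "sample size, mean, standard deviation, minimum and maximum (and others as needed) for continuous variables) at each respective time point".
- Section 9.5: "Only actual data will be analyzed; there will be no imputation of missing data".
- Section 9.6: "The primary endpoint analysis and all secondary endpoint analyses will be carried out on the Per Protocol analysis set". To enter that set, besides receiving the tibial base without a meaningful eligibility deviation, Section 9.6.3 asks only that "The subject has at least one post-operative evaluation in the 6 week or later time window". A subject can therefore count at 6 weeks and be absent at 5 years.

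Two rules decide who is absent. Under Section 8.6, if the femoral component or tibial base is revised, "the Subject is to be withdrawn from study participation". Section 8.5 adds: "No data after the date of withdrawal will be included in the clinical analysis".

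No repeated-measures model, comparison of leavers with stayers, or missing-data sensitivity analysis is planned.

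**The concern.** Each subject can contribute up to five post-operative scores, but each visit is summarised on its own. A subject who leaves after 2 years counts at the visits attended, and those scores play no part in the 5-year estimate. The 1-, 2- and 5-year means can therefore come from different groups of people. A mean that holds or rises between visits may do so merely because poorer knees have left.

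Observed-case means are unbiased only if leaving is unrelated to how the knee is doing. The protocol breaks that condition for one group by design: subjects whose femoral component or tibial base is revised are withdrawn and their later scores excluded.

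Section 6.2 presents these endpoints as evidence of surgical effectiveness, and Section 7 gives mid-term outcomes as a reason for follow-up to 5 years. Section 9.8.4 also reports each endpoint by configuration and by primary or revision procedure, so unequal retention could look like a difference in PROMs. A larger sample does not reduce this bias.

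**Working it through.** **1. The plan's own figures.** The only sample-size figures are for the primary endpoint (Section 9.7). With p0 = 0.85, p1 = 0.91, one-sided alpha 0.05 and power 0.80:

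n = [(1.645 × √(0.85 × 0.15) + 0.842 × √(0.91 × 0.09)) / 0.06]² = 190.5, so 191. Allowing for 15% attrition, 191 / 0.85 = 224.7, so 225.

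Both figures reproduce. They concern the 1-year responder rate and say nothing about the PROM means. The 15% is a 1-year allowance; no figure is given for 2 or 5 years.

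**2. Bias of an observed-case mean.** Let m be the share missing. The full mean is (1 − m) × (mean of stayers) + m × (mean of leavers). Subtracting this from the mean of stayers gives:

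bias = m × (mean of stayers − mean of leavers).

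Only the 600 subjects and the 15% come from the documents. The other shares, and every gap, are assumptions.

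| Share missing | Observed of 600 | Gap 5 points | Gap 10 points | Gap 20 points |
|---|---|---|---|---|
| 15% | 510 | 0.75 | 1.5 | 3.0 |
| 25% | 450 | 1.25 | 2.5 | 5.0 |
| 35% | 390 | 1.75 | 3.5 | 7.0 |

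**3. Simulation with a stated mechanism of loss.** Assumptions, none from the documents except N: 600 subjects, SD of change 20 points, 2-to-5-year correlation 0.5 or 0.7, 15% or 31% missing at 5 years, and log-odds of loss rising by 0.35 or 0.55 per SD worse. The likelihood estimate uses the 2-year scores of everyone, including those missing at 5 years. Results are bias in the 5-year mean change, in points, with 2,000 runs per setting.

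| Loss depends on | Observed-case bias | Likelihood bias |
|---|---|---|
| 2-year score (observed) | +0.5 to +2.2 | within 0.04 of zero |
| 5-year state (unobserved) | +1.0 to +3.2 | +0.5 to +2.4 |

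In the first row, leavers were about 0.34 to 0.53 SD worse at 2 years. The formula in step 2 agrees with the simulation: at 31% missing, correlation 0.7 and log-odds 0.55, the 5-year gap was 7.27 points, and 0.31 × 7.27 = 2.25 against a simulated 2.23. In a companion run with loss unrelated to outcome, the observed-case bias was about zero.

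**4. What the second row means.** Under Section 8.2.4.1 no PROMs are collected at the year 3 and 4 contacts. Worsening after year 2 that leads to loss leaves no score for a model to use. The near-zero bias in the first row follows from the mechanism assumed there and is not a forecast of what the model would deliver.

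**The case against.** The strongest case is that nothing is decided on these means. They are descriptive and single-arm, Section 9.4 says the primary test is the only hypothesis, and success is the 1-year responder rate against 85%. A bias of 0.5 to 3 points is small beside the 10-point individual improvement in the responder definition, although that is not a margin for group means. The protocol also works to limit loss: mailed PROMs with a phone contact, wide continuous windows, at least three contact attempts, and continued follow-up after insert exchange or patella revision under Section 8.6. N is reported at each visit, and survivorship is reported separately by Kaplan-Meier on the Safety set.

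Much of this stands. It limits how much the point matters. It does not correct the means: retention efforts lower the share missing, and Kaplan-Meier counts revisions but says nothing about unrevised subjects who stop responding.

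Three stronger readings are tempting, and the documents do not support them.

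- A reader might infer that the 5-year means will be too high. Apart from component revision, nothing shows that leavers do worse. If subjects who are doing well stop attending, the bias runs downward.
- A reader might infer that the study would report 95% intervals with poor coverage. Sections 9.4 and 9.8.4.2 specify no interval for PROM means.
- A reader might infer that a likelihood model removes the bias. Step 4 shows that it may not.

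**Conclusion.** The point holds as a gap in the analysis of descriptive secondary endpoints. As planned, the 2- and 5-year mean PROM changes describe the subjects still present, and they are too favourable if those doing worse leave. Part of the loss is tied to outcome through the withdrawal rule for femoral or tibial-base revision.

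The size cannot be fixed from the documents. With an assumed SD of 20 points and 15-31% missing at 5 years, the overstatement is roughly 0.5-2 points if loss depends on the 2-year score and 1-3 points if it depends on the 5-year state. It is about zero if loss is unrelated to outcome. The primary endpoint and its sample size are unaffected. A repeated-measures model is worth adding because it is cheap and rests on a weaker assumption than the observed-case means.

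**What to change.** In Section 9.8.4.2:

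1. Keep the observed-case summaries and show expected and observed N at each visit.
2. Add a mixed model for repeated measures on all observed post-operative scores for the KOOS sub-scores, AKS and EQ-5D-5L. Fixed effects: visit, baseline score, baseline-by-visit, configuration, and primary or revision procedure; unstructured covariance. Report adjusted mean change with a 95% CI at each visit.
3. Add a matching model for FJS-12 using post-operative scores only, since it has no pre-operative value.
4. State that the model estimates refer to subjects alive with the femoral and tibial-base components in place, and that they are read beside the Kaplan-Meier results. Without this, the model silently treats revised or deceased subjects as if the implant were still in place.
5. Add a sensitivity analysis that gives unfavourable values to missing scores. Because Section 9.5 rules out imputation, it needs a short exception there. The mixed model imputes nothing and needs none.

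Separately, reconcile Section 8.5, which lists revision of any study component as a withdrawal, with Section 8.6, which keeps subjects in the study after insert exchange or patella revision. The answer decides whose later PROMs are counted.

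The cost is plan wording and modest programming, with no new data or visits. The downside is that the model relies on data being missing at random, and it reduces but does not remove bias when worsening after year 2 drives the loss.

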6.3 Tertiary Objectives

• Implant survivorship of the ATTUNE Cementless FB Tibial Base using Kaplan-Meier survival analysis at 3 and 4-year timepoints.

The primary and secondary clinical endpoints and the relevant statistical analyses are described in detail in **Section 9**.

Table 6-1: Summary of Primary and Secondary Objectives with Respective Endpoints

	Outcome	Endpoint Timing
	Functional Responder rates are expected to be between 91%-94% where subject shows 20% improvement from baseline and 10 points improvement from baseline in at least 2 of the following categories:	
	KOOS (ADL)	
Primary	KOOS (Pain)	1 year
Endpoint	 KOOS (Quality of Life) The Objective performance criteria is expected to be 85%. The primary endpoint will be performed for 225 tibia (CR FB and PS FB combined) implanted as primary TKA procedures. Study success will be determined using the primary TKA (CR FB and PS FB combined) analysis group. 	
	Type and frequency of Adverse Events and Device Deficiencies for non-screen failed subjects.	Intraoperative through to end of study
Secondary Endpoints	Functional responder rates with an objective performance criteria (OPC) of 85% as measured by the KOOS questionnaire for all subjects.	1 year
Linupolitis	Change from pre-op baseline in AKS (2011), KOOS (all subscores), and EQ-5D-5L and change from first post-operative visit to all other post-operative visits for FSJ-12.	6 week, 6 months, 1, 2 and 5 years
	Survivorship	1, 2 and 5 years
	Radiographic Interface Analysis	1, 2 and 5 years

7 STUDY DESIGN

This study is designed as a post-market, prospective, multi-center, non-randomized, non-comparative, single arm observational study. Level of evidence: III. The sample size for this study is anticipated to be a minimum of 600 subjects. A minimum of each of the following variants must be included:

- 300 ATTUNE Cementless Cruciate Retaining Fixed Bearings
- 300 ATTUNE Cementless Posterior Stabilizing Fixed Bearings
- Up to 300 ATTUNE Cementless Patellae (if available in United States market during the clinical study)

There will be a maximum of 25 sites in the United States. The study will allow for a minimum of 600 subjects to be implanted: 300 ATTUNE Cementless Cruciate Retaining Fixed Bearing (CR Femoral with CR or MS Tibial Insert) TKAs, 300 ATTUNE Cementless Posterior Stabilizing Fixed Bearing (PS Femoral with PS Tibial Insert) TKAs, and up to 300 ATTUNE Cementless Patellae (if market available) will be included in the DSJ_2019_05, Rev D (FINAL)

DePuy Synthes Products, Inc. - Confidential 24 August 2022

total sample. It is expected that each site will implant approximately 30 subjects (maximum of 50 per site). Treatment assignment in this study is not randomized. Sites are able to enroll subjects with the required variants, any allowed configuration until the minimum of 300 cases for that variant (CR FB or PS FB) is met. Once the cases for any particular variant are met, sites will continue to enroll the remaining variants until their site maximum of 50 subjects is met. Details regarding sample size are presented in Section 9.7.

The Sponsor will monitor overall project enrollment. The Sponsor can authorize a shift of a group of Subjects from one site to another to maintain project timelines. For example, the Sponsor can reduce the cohort of a slow-enrolling site to a faster-enrolling site and the faster-enrolling site will assume responsibility for the reallocated cohort.

Primary Endpoint analyses will be conducted after 225 patients who have undergone TKA have passed the 1 year preferred window for submission to regulatory authorities. The remaining follow-up through 5 years will further evaluate mid-term outcomes and support post-market clinical follow-up commitments.

The Investigator should follow their current standard of care with respect to patellar resurfacing. Specifically, the Investigator can choose to:

- resurface the patella with a cemented ATTUNE patella.
- leave the patella unresurfaced.

When the ATTUNE Cementless Patella becomes available to the Sites, the Investigator can choose to:

- resurface the patella with an ATTUNE Cementless Patella.
- resurface the patella with a cemented ATTUNE Patella.
- Leave the patella unresurfaced.

